#### Vital sign and Physical Exam

• Vital sign and physical exam abnormalities will be summarized. The data listings of individual abnormalities will be provided.

#### Urine Pregnancy Test

• Urine pregnancy test results will be listed by subjects.

Sections 4.1.2 and 4.2.2 list the summary tables and data listings planned for blinded phase. Sections 5.1.2 and 5.2.2 list the summary tables and data listings planned for open-label phase.

#### 3.3.2 *Efficacy Analysis*

Since the study was terminated early, no efficacy analysis planned for the study report, while safety data will be summarized and reported in the study report.

However, with careful review of the mammographic data after database lock, mammographic efficacy data may be analyzed as ad-hoc analyses as necessary.

#### 3.3.3 Subgroup analyses and Multiplicity adjustment

• Multiplicity adjustment will not be applied for multiple testing in this study.

#### 3.4 Handling of Missing Data

#### 3.4.1 Imputation of Missing Date for Safety Analyses

For safety analyses, the incomplete date and time for the safety events will be imputed using the following rules.

- Missing start time of an AE reported on the first dose day will be imputed as dose time + 1 minute, and the AE will be considered as Treatment emergent AE (TEAE).
- Missing start time of an AE other than the first dose day will be imputed as 00:01 (hh:mm).
- Missing end time of an AE other than the first dose day will be imputed as 23:59 (hh:mm).
- Missing start date of any AE will be imputed as the 1st of the month.
- Missing end date of any AE will be imputed as the last day of the month.

If the severity of an AE is missing, then the AE will be considered as "Severe". If the relationship to the study agent of an AE is missing, then the AE will be considered as "Related" to study agent.

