## 7.3 Blinded Phase Visits

• Study Week 1: Telephone Call (+/- 1 day)

During this visit, the site will call the subject and review the subject's dosing compliance, product application, and query for any AEs.

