#### 8.0 ASSESSMENTS OF SAFETY

#### 8.1 Adverse Event Collection and Reporting

#### • Adverse Event Collection

AEs will be captured for the duration of the study. The reporting period begins with the first dose of study drug (Study Day 1) and ends at Week 52 and Week 104. The Adverse Events eCRF must be completed for all reported AEs and SAEs.

For this study, an AE is defined as: "Any untoward medical occurrence in a patient or clinical investigation subject administered a pharmaceutical product and which does not necessarily have a causal relationship with this treatment." This includes any newly occurring event or previous condition that has increased in severity or frequency since the administration of study drug.

AEs may also be reported spontaneously at any time. Details of any adverse or unexpected events, signs, and symptoms will be collected including details of onset, resolution, frequency, severity (as defined below), seriousness, relationship to the drug, effect on the study drug, treatments administered, and outcome. Any AE will be followed, whenever possible, until it returns to the baseline condition or becomes stable with no further change expected.

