#### • Pre-existing Conditions

Pre-existing conditions (present before the start of the AE collection period) are considered concurrent medical conditions and should NOT be recorded as AEs. However, if the subject experiences a worsening or complication of such a concurrent condition, the worsening or complication should be recorded as an AE. Investigators should ensure that the AE term recorded captures the change in the condition (e.g., "worsening of....").

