#### Adverse Events

- All adverse events (AE) will be summarized with MedDRA primary system organ class (SOC) and preferred term.
- Summary tables of severe AEs, SAEs and study drug related AEs will also be provided.
- Listings of all AE, serious adverse events (SAE), and severe AEs will be provided.

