#### **Important Derived Variables:**

- Age = (Screening Date Date of Birth +1)/365.25.
- Prior Medications and Treatments: the medications and treatments started before the subject was enrolled to the study without any change after enrollment.
- Concomitant Medication and Treatments: the medications and treatments started after the subject was enrolled to the study. Any medications and treatments started before enrollment but changed after enrollment will be considered as concomitant medications and treatments.
- Baseline: All clinical measurements (safety and efficacy data) collected at Day 1 or before the first dose will be analyzed as baseline. One baseline is for both blinded phase and open-label phase.
- Post Baseline: All clinical measurements (safety and efficacy data) collected after the first dose will be analyzed as post baseline. For blinded phase, the scheduled post-baseline visits are at Week 13, 26, 39 and 52. For open-label phase, the scheduled post-baseline visits are at Week 65, 78, 91 and 104.
- Study Drug Compliance by Visit

 $\frac{\text{Weight (g) of dispensed canisters} - \text{Weight (g) of returned canisters}}{3.52\text{g} \times \text{ number of days between visits}} \times 100\%,$ 

- The number of days between visits = the date of current visit the date of last visit +1
- $\circ\,$  Drug compliance will be calculated only for the subjects who returned all canisters dispensed.
- Overall study drug compliance of the study phase will be the average of visit compliance
- Treatment emergent Adverse Events (TEAE): Any AEs started on or after the day of the first study drug dosed.

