#### 4. OUTPUT PLANNED FOR THE STUDY REPORT (BLINDED PHASE)

#### 4.1 **Tables to be Included in Study Report**

In the following sections, the different results are presented in the order in which it is planned to make them appear in the study report.

The table templates are available in the Appendix of the SAP. The content shown in the templates are an example only. It is not based on real study data or details concerning design.

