# 4.1.2 Summary of safety endpoints

- 9. Table [TAE01a] Summary of Adverse Events (Blinded Phase) Safety Population
- 10. Table [TAE02a] Number (%) of Subjects with Adverse Events by Body System and Preferred Term (Blinded Phase) – Safety Population
- 11. Table [TAE03a] Number (%) of Subjects with Serious Adverse Events by Body System and Preferred Term (Blinded Phase) Safety Population
- 12. Table [TAE04a] Number (%) of Subjects with Severe Adverse Events by Body System and Preferred Term (Blinded Phase) Safety Population
- 13. Table [TAE05a] Number (%) of Subjects with Study Agent Related Adverse Events by Body System and Preferred Term (Blinded Phase) Safety Population
- 14. Table [TAE06a] Number (%) of Subjects with Adverse Events by Preferred Term and Overall Frequency (Blinded Phase) Safety Population
- 15. Table [TVS01a] Summary of Vital Signs and Change from Baseline (Blinded Phase) Safety Population
- 16. Table [TPE01a] Summary of Physical Examination (Blinded Phase) Safety Population
- 17. Table [TLB01a] Summary of Laboratory (Hematology) Test Results Safety Population
- 18. Table [TLB02a] Summary of Laboratory (Blood Chemistry) Test Results Safety Population
- 19. Table [TLB03a] Summary of Urine Pregnancy Test Results (Blinded Phase) Safety Population

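### The AE start-date rule has no floor at first dose, so missing-day events in the first-dose month are nearly all dated before treatment and fail the TEAE definition

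*SAP*

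**What the plan says.** SAP 3.4.1 gives the rule for incomplete AE dates: "Missing start date of any AE will be imputed as the 1 st of the month". It applies to any AE. The one provision in that list tied to dosing covers a missing start time on the first-dose day. Such an event is placed one minute after the dose and counted as treatment-emergent. A missing day has no such protection.

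SAP 3.7 (Important Derived Variables) makes the flag depend on the start date: "Treatment emergent Adverse Events (TEAE): Any AEs started on or after the day of the first study drug dosed".

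Protocol 8.1 fixes when AE collection starts: "The reporting period begins with the first dose of study drug (Study Day 1) and ends at Week 52 and Week 104". Protocol 8.2 keeps earlier conditions out of the AE data: "Pre-existing conditions (present before the start of the AE collection period) are considered concurrent medical conditions and should NOT be recorded as AEs".

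On outputs, SAP 3.3.1 states: "All adverse events (AE) will be summarized with MedDRA primary system organ class (SOC) and preferred term". The AE table titles in SAP 4.1.2 also refer to adverse events without a treatment-emergent restriction. The shells are elsewhere: "The table templates are available in the Appendix of the SAP". They are not in the text available for this review.

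**The concern.** By the protocol's collection rules, a recorded AE is an on-treatment event. If only its month is known and that month is the month of first dose, its true onset lies between the first-dose date and the end of the month. The SAP rule puts it on the 1st. Unless dosing began on the 1st, that date is before treatment, and the event is classed as not treatment-emergent. The rule therefore gives a date and a flag that contradict what the protocol says about the same event.

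It also runs against the rest of SAP 3.4.1, which sets missing severity to severe, sets missing relationship to related, and protects first-dose-day events with a missing time. SAP 3.8 says the report on the terminated study will focus on safety and PK/PD, so AE derivations carry more of its weight than they would in a full efficacy report.

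**Working it through.** The documents give no figure for this point, so there is nothing to reproduce. The check is how often the rule gives a pre-dose date.

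**Inputs from the documents.** The 1st-of-month rule (SAP 3.4.1), the TEAE definition (SAP 3.7), AE collection from first dose (Protocol 8.1) and 52 weeks of blinded treatment.

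**Assumptions.** First-dose dates are spread evenly over the calendar, AE onset is even over treatment, and at first a missing day is equally likely at any time.

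**Share within the first-dose month (30-day month).** With first dose on day *d*, the possible onset days in that month number 31 − *d*.
- All possible onset days: sum over *d* = 1 to 30 of (31 − *d*) = 465.
- Days not misdated (first dose on the 1st): 30.
- Misdated share: (465 − 30)/465 = 435/465 = 93.5%.

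For 28- and 31-day months the same formula, 1 − 2/(L + 1), gives 93.1% and 93.8%. If onset is concentrated soon after dosing (exponential decay, 7-day scale), the share is 95.5% to 96.0%. Enumerating every first-dose date over 1,461 consecutive days gives 93.6%. The imputed date then falls on average 10.5 days, and at most 30 days, before first dose.

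**Share of all missing-day AEs.** Affected days per subject = 435/30 = 14.5.
- 52 weeks: 14.5/364 = 4.0%
- 26 weeks: 14.5/182 = 8.0%
- 13 weeks: 14.5/91 = 15.9%

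The enumeration gives 4.0%, 8.1% and 16.2%. The 26- and 13-week rows are illustrations only. SAP 1.3 reports shorter treatment for a large proportion of subjects but gives no durations.

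**Better recording early on.** The supervised first dose and the calls at Weeks 1 and 4 should make missing days rarer at the start. Let a missing day in the first 28 days be *f* times as likely as later. For a 30-day month, 434 of the 435 affected days fall in the first 28 days of treatment, so

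share = [(434*f* + 1)/30] / [28*f* + (days − 28)].

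For *f* = 0.5 over 52 weeks this is 7.27/350 = 2.1%. For *f* = 0.25 it is 3.65/343 = 1.1%. The full enumeration gives:

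| Treatment length | *f* = 1 | *f* = 0.5 | *f* = 0.25 |
|---|---|---|---|
| 52 weeks | 4.0% | 2.1% | 1.1% |
| 26 weeks | 8.1% | 4.4% | 2.3% |
| 13 weeks | 16.2% | 9.6% | 5.3% |

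Per 50 missing-day AEs (an assumed count), this is 0.5 to 2.0 events over 52 weeks, 1.2 to 4.0 over 26 weeks and 2.7 to 8.1 over 13 weeks. A higher AE rate soon after dosing would raise these shares. The documents give no figure for that, so none is used.

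**After the fix.** With the imputed date set to the later of the 1st and the first-dose date, none of these events is dated before treatment, whatever the dosing day or month length.

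**The case against.** The strongest reply is that no stated output depends on the flag. The AE summaries, table titles and listings all refer to adverse events, and the term TEAE appears only in the dose-day time rule and in its own definition. Since AEs are collected only from first dose, the all-AE set is already the intended set, and a wrong flag removes nothing from it. Any lost event depends on table shells that cannot be seen here. This stands, and it limits the consequence. It does not make the derived date or flag correct.

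A second reply is that the number of missing days is unknown. Early calls, the supervised first dose, and the data queries and completeness checks in Protocol 9.5 should keep it low. This also stands. The number could be zero, and the per-50 figures only show scale. But the SAP includes a rule for such dates, and the rule should give the right answer when it is used.

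A third reply is that the proposed change leaves other gaps. The same rule could move an event back across the start of open-label dosing, no rule is stated for assigning AEs to phases, and a wholly missing start date has no rule. These are real but separate, and they do not undo the point about first dose.

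**Conclusion.** The concern holds, as a minor point. Followed as written, SAP 3.4.1 gives a wrong start date and a wrong TEAE flag to any recorded AE with a missing day in the first-dose month, unless dosing began on the 1st. Nothing else in the SAP or protocol repairs this. About 94% of such events are affected, and the figure stays between 93% and 96% across the month lengths and onset patterns tried. It would change materially only if first doses clustered on the 1st.

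The share of all missing-day AEs, about 1% to 4% over 52 weeks, is less firm because it rests on the assumed timing of onset and of missing days. Confidence is high that the rule is wrong. The effect on any reported table is not shown, and no direction of bias between arms is claimed.

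**What to change.** Add one sentence to SAP 3.4.1: when the start day is missing and the known month and year are those of first dose, impute the later of the 1st of the month and the first-dose date, unless a recorded end date shows that the event began earlier.

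The cost is that sentence and about one line of code. The downside is that an event that truly began before first dose, but was recorded as an AE with a missing day and no earlier end date, would be flagged as treatment-emergent. Protocol 8.1 and 8.2 keep such events out of the AE data, so this should be rare. It also errs in the same cautious direction as the severity and relationship rules in that section.

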#### 3.4.2 Imputation of Missing Data for Efficacy Analyses

The study was terminated early so no statistical methods will be implemented for imputing missing data. The statistical analysis will focus on descriptive statistics of observed data.

#### 3.5 **Protocol Deviations**

Listing for all protocol deviations will be provided.

Listing for major deviations that result in excluding from the PP population will also be provided for blinded phase.

See sections 4.2.1 and 5.2.1 for the data listings planned for blinded phase and open-label phase.

#### 3.6 **Pharmacodynamic and Pharmacokinetic (PD/PK) Data**

- Bone biomarkers (CTx and BSAP) level and change from baseline will be summarized by visit and treatment group. Individual data listing will also be provided.
- Plasma concentration of study agent (4-OHT E&Z isomers) will be summarized by visit and treatment group. Individual data listing will also be provided.
- Hormones (FSH, Estradiol and Estrone) will be summarized by visit and treatment group. Individual data listing will also be provided.
- Coagulation parameters (Protein C Activity, Protein C antigen, Protein S antigen total, Protein S antigen free, Antithrombin III antigen, Activated protein C resistance) will be summarized by visit and treatment group. Individual data listing will be provided as well.

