#### 1.2 Design

This is a multi-center, randomized, double-blind, placebo-controlled study in women identified as having dense breast tissue upon screening mammography.

Subjects who give informed consent will have screening evaluations, including hormone measures of FSH, Estradiol and Estrone to determine menopausal state. Those subjects meeting entry criteria, will be stratified, based on their hormone levels, into pre/peri and post menopause groups and randomized within those groups 2:1 to receive either 8 mg/day (4 mg/breast) BHR-700 gel or placebo for up to 52 weeks. At the Principal Investigator's (PI) discretion, subjects may be allowed to reduce the dose to 4 mg/day (2 mg/breast) in cases of intolerance.

Subjects will apply the gel to both breasts once per day. The first dose will be applied under the supervision of the PI/designee. Subsequent doses will be self-administered daily by the subject until she has completed 52 weeks of study drug administration. Study drug compliance will be checked at each study visit. Subjects will be asked to capture daily gel administration in a diary and drug canisters will be weighed on release to the subject and on return. The canister weight will be recorded in grams. If the study drug is discontinued or interrupted, the reason(s) will be recorded. During treatment period, subjects will be evaluated at Day 1 and every 13 weeks (±2 weeks) thereafter.

A planned sample size of 330 women, identified as having dense breast tissue upon screening mammography, will be randomized to receive either BHR-700 gel or placebo (at 2:1 ratio). Considering an attrition rate of approximately 15%, it is expected to have 272 evaluable women (4-OHT: 181 & Placebo: 91) who will have both baseline and 52 week measurements of percent mammographic density (MD) of the breast.

Subjects who complete the double-blind phase of the study will be offered entry into an open-label follow-up period for an additional 52 weeks.

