#### 2.2.2 Secondary Endpoints

- 1 The percentage reduction in breast density at Week 52 using two breast density measurement methods (Cumulus versus Volpara).
- 2 The percentage of women who underwent a change in BI-RADS category when comparing pre-and post-treatment measurements.
- 3 The percentage of women with a ± 10% absolute decrease in quantitative mammographic density (Cumulus) between baseline and 52 weeks,
- 4 Change in serum concentration of: cholesterol, triglycerides, high-density lipoprotein (HDL), and low-density lipoprotein (LDL).
- 5 Change in serum concentration of sex hormone binding globulin (SHBG).
- 6 Change in serum concentration of Protein C-activity, Protein S-activity, Antithrombin 111 antigen, and Activated Protein C resistance (APCR).
- 7 Change in serum concentration of select bone biomarkers CTx and BSAP.
- 8 Incidence and severity of AEs and laboratory values.
- 9 The menstrual cycle of premenopausal women.
- 10 Pharmacokinetic (PK) plasma concentration of the E and Z isomers of 4-OHT after 13, 26, 52, 78, and 104 weeks of application of 4 mL BHR-700 gel to the breasts.

The secondary endpoints are for both blind and open-label treatment phases.

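### The analyte lists in SAP 3.6 do not match secondary endpoints 5 and 6: SHBG and Protein S activity are missing, and three antigen assays appear that are declared nowhere else

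*SAP*

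**What the plan says.** SAP 2.2.2 declares four groups of laboratory secondary endpoints, each defined as a change. Two of them matter here. Item 5 is "Change in serum concentration of sex hormone binding globulin (SHBG"). Item 6 is "Change in serum concentration of Protein C-activity, Protein S-activity, Antithrombin 111 antigen, and Activated Protein C resistance (APCR"). The protocol synopsis declares the same two endpoints.

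SAP 3.6 then says what will be summarised as pharmacodynamic data:

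- Coagulation: "Coagulation parameters (Protein C Activity, Protein C antigen, Protein S antigen total, Protein S antigen free, Antithrombin III antigen, Activated protein C resistance"), by visit and treatment group.
- Hormones: "Hormones (FSH, Estradiol and Estrone) will be summarized by visit and treatment group".
- Bone markers: "Bone biomarkers (CTx and BSAP) level and change from baseline will be summarized by visit and treatment group".

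The three hormones in 3.6 are the ones that SAP 1.2 describes as "hormone measures of FSH, Estradiol and Estrone to determine menopausal state". None of them is an endpoint.

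The laboratory list in SAP 3.7 includes SHBG and luteinizing hormone under hormones, and Protein S activity under coagulation factors. SAP 3.8 says that the shortened report will concentrate on safety and PK/PD results. It records no change of assays.

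**The concern.** No efficacy analysis is planned for the study report (SAP 3.3.2), so safety and PK/PD make up most of what it will contain. SAP 3.6 is the text that tells the programmer which PD analytes to summarise and how. Where its lists differ from the declared endpoints, a declared endpoint can drop out of the report without anyone having decided to drop it.

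The coagulation mismatch is also ambiguous. SAP 3.6 itself treats activity and antigen as separate measurements, since it lists Protein C both ways. For Protein S it names two antigen measurements and no activity. A reader cannot tell whether this is a drafting slip or whether the laboratory ran different assays from those declared.

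The analytes carry some weight in this trial. The protocol synopsis lists coagulation factors among its additional important safety parameters. Protocol 2.2 supports the topical route partly by citing smaller effects on endocrine and coagulation parameters than with oral tamoxifen.

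**Working it through.** The plan gives no figure to reproduce. The check is a comparison of lists.

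**Coagulation.** The declared list is the same in SAP 2.2.2 item 6, SAP 3.7, the protocol synopsis, protocol Appendix 1 and protocol Appendix 4.

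| Analyte | Declared list | SAP 3.6 |
|---|---|---|
| Protein C activity | yes | yes |
| Protein S activity | yes | **no** |
| Antithrombin III antigen | yes | yes |
| Activated protein C resistance | yes | yes |
| Protein C antigen | no | **yes** |
| Protein S antigen, total | no | **yes** |
| Protein S antigen, free | no | **yes** |

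Declared: 4. Named in 3.6: 6. In common: 3. Declared but not in 3.6: 4 − 3 = 1. In 3.6 but not declared: 6 − 3 = 3. Antithrombin III antigen is declared throughout, so it is not one of the three.

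**Hormones.** The measured list comes from SAP 3.7 and protocol Appendix 4, and Appendix 1 schedules the same five.

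| Hormone | Measured list | Endpoint in SAP 2.2.2 | SAP 3.6 |
|---|---|---|---|
| FSH | yes | no | yes |
| Estradiol | yes | no | yes |
| Estrone | yes | no | yes |
| LH | yes | no | **no** |
| SHBG | yes | **yes (item 5)** | **no** |

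Measured: 5. Named in 3.6: 3. Omitted: 5 − 3 = 2. One of the two omitted is an endpoint, and none of the three named is. Appendix 1 gives SHBG its own row, pre-dose and at Week 52 in the blinded phase.

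**Form of the summary.** Items 5 and 6 are changes in concentration. In SAP 3.6 only the bone-marker bullet promises level and change from baseline. The hormone and coagulation bullets promise a summary by visit and treatment group and do not mention change.

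**Does other text supply what is missing?**

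- SAP 3.3.1 promises change from baseline for haematology and blood chemistry. Neither SHBG nor Protein S activity belongs to those panels in SAP 3.7 or Appendix 4.
- SAP 3.7 lists both analytes as laboratory assessments but specifies no summary of them. It shows that the SAP disagrees with itself.
- SAP 4.1.3 and 4.2.3 plan hormone and coagulation tables and listings under generic titles that name no analyte.
- Protocol 9.1 says that laboratory parameters will be summarised descriptively, without naming any. It also gives the SAP precedence where the two are inconsistent.
- SAP 3.8 records no substitution or removal of assays.

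None of these resolves the conflict.

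**The case against.** The strongest reply is that nothing need be lost. SAP 3.6 does not say that its lists are exhaustive, and 2.2.2 still declares both endpoints. Hormone and coagulation tables and listings are planned, and 3.7 places SHBG and Protein S activity under those headings. The table shells attached to the SAP could name every analyte, but they are not in the readable text. The emphasis after termination is descriptive (SAP 1.3), so no test or error rate depends on the lists. This reply stands as a limit on the consequence. It does not remove the conflict, because 3.6 chose to name analytes and its names disagree with 2.2.2 and 3.7.

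Three stronger readings are tempting, and the documents do not support them.

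- A reader might infer that SHBG and Protein S activity will be absent from the report. The generic titles and unseen shells leave that open.
- A reader might infer that the data for both are in hand because Appendix 1 schedules them. Scheduled is not the same as collected. The SAP was written after termination and relies on what is in the clinical database. The antigen assays may have replaced Protein S activity.
- A reader might want a share of all laboratory endpoint analytes left uncovered. Items 4 to 7 contain 4 + 1 + 4 + 2 = 11. If panel headings count, as they must for the lipids in item 4, all 11 are covered. If only analytes named in 3.3.1 and 3.6 count, 3 coagulation + 2 bone = 5 are. The share depends on the rule, so it is not a useful measure.

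**Conclusion.** The inconsistency is real and plain on the page. SAP 3.6 omits SHBG, the whole of secondary endpoint 5, and Protein S activity, one of the four components of endpoint 6. It also omits LH, which is measured but is not an endpoint. It names three antigen assays found nowhere else in the readable text, and it does not promise the change from baseline by which endpoints 5 and 6 are defined.

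The consequence is a possible omission of declared endpoints from a descriptive report. It is not a wrong inference. This rests on two conditions: the shells may or may not name the missing analytes, and the documents do not show which assays were actually run. The point should be corrected because 3.6 governs the PD content of the report and the repair is small.

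**What to change.** First check every hormone and coagulation assay in question against the clinical database: SHBG, LH, Protein S activity and the three antigen assays. Then align SAP 3.6 with 2.2.2 and 3.7:

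- Add SHBG and LH to the hormone bullet, and Protein S activity to the coagulation bullet.
- For SHBG and the four endpoint 6 analytes, state level and change from baseline by visit and treatment group, as the bone-marker bullet already does.
- Delete the three antigen assays if they were not run. If they were, keep them and label them as additional analytes.
- If a declared assay was not run or was replaced, for example Protein S antigen in place of activity, say so in 3.8 and do not promise that summary in 3.6.
- Confirm that the hormone and coagulation table shells carry the same lists.

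The cost is one check of the assay list, a rewording of two bullets, and an entry in 3.8 if the check shows a departure from the declared assays.
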